12.2.5 Determination of Patients/Data for Analysis

All 1.5 prevention and secondary prevention subjects with an ICD/CRT-D implant will be included in the primary analysis hypothesis test. This includes subjects implanted with a device after the initial enrollment period. These later implants will be included if they are secondary or 1.5 at the time of implant.

12.2.6 Sample Size

A simulation program was written to determine the sample size for the study.

Assumptions are based on the OMNI data and estimates from steering committee physicians:

- 60% of enrollments will be secondary prevention and 40% primary prevention
- 50% of primary subjects will be in the 1.5 group
- 57% of secondary subjects will get an ICD (includes CRT-D)
- 45% of 1.5 subjects will get an ICD
- 22% of 1.0 subjects will get an ICD
- Annual attrition (includes exits and deaths) will be 10%
- The study will end two years after the last enrollment

- 4000 patients will take 2 years to enroll with enrollment beginning slowly, then accelerating to a steady 246 per month.
- Expected rates of appropriately treated VT/VF in secondary subjects follow Figure 2, with a higher rate in the first year (22.5%), then a constant rate (11.1%) thereafter.
- The hazard ratio of 1.5 to secondary is 0.91

Under the above assumptions and using the hypothesis test stated above, 4800 subjects will have 80% power to reject the null hypothesis. With 4800 enrolled patients, it is expected that approximately 1650 secondary prevention subjects will be implanted, 430 1.5 prevention subjects will be implanted, and 200 1.0 subjects will be implanted.

12.2.7 Sample Size Re-estimation

Because most of the assumptions above are based only on investigator opinion, the sample size will be re-estimated during the study using the same simulation methods, but changing the following assumptions using the study data:

- % of enrollments will be secondary prevention
- % of primary patients in the 1.5 group
- % of secondary patients who will get an ICD (includes CRT-D)
- % of 1.5 patients who will get an ICD
- % of 1.0 patients who will get an ICD
- Annual attrition (includes exits and deaths)
- Enrollment rate

With this re-estimation of sample size, the length of follow-up after the last enrollment may be changed as well.

Because no comparisons will be done at the point of re-estimation, alpha is not affected and the final analysis can compare the p-value to a 0.05 alpha level.

The sample size re-estimation will occur at the later of:

- One year after the 400th subject has been enrolled
- The time of the 2000th enrollment.

It is the study sponsor's discretion to increase (to a maximum of 8000 subjects) or decrease the sample size, or decrease or increase the length of follow-up after last enrollment.

If fewer subjects are required, the study sponsor may either lower the sample size, or increase the power of the study (possibly keeping the original sample size). If more subjects are required, the study sponsor may elect to not increase the sample size, but may increase the length of follow-up to ensure adequate power for the study.

Study sites will be notified of any change in sample size and length of follow-up (if applicable) at that time. The investigational plan will not be changed.

12.3 Secondary Objective: Mortality

Compare the mortality rates for patients meeting 1.5 prevention criteria between those implanted with a device (ICD/CRT-D) and those not implanted.

12.3.1 Hypothesis

Although this is an exploratory objective and is not powered, a hypothesis test will be done and compared to an alpha level of 0.05. To preserve overall type I error, this test is only valid if the primary endpoint is statistically significant.

Compare the mortality rates for patients meeting 1.5 prevention criteria between those implanted with a device (ICD/CRT-D) and those not implanted.

H_0 : Hazard ratio of non-implanted to implanted 1.5 patients = 1

H_A : Hazard ratio of non-implanted to implanted 1.5 patients $\neq 1$

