12.2.4 Analysis Methods

The hypothesis will be tested using a Cox proportional hazards model with survival time and first appropriate VT/VF episode as the dependent variable and group (secondary or 1.5) as the independent variable. A 95% one-sided lower confidence bound for the hazard ratio and a p-value will also be calculated. The data will be presented in a format similar to the right panel of Figure 2.

Adequate power is needed to perform the hypothesis test. Without adequate power, a non-significant test has little meaning. Therefore, the hypothesis test will not be performed and a p-value will not be calculated if there are fewer than 400 subjects in the implanted 1.5 prevention group. In that case, event rates and confidence intervals will be presented.

Time 0 will be the implant date and subjects will be censored on the date of their latest device interrogation. Only spontaneous, appropriately treated VT/VF episodes as adjudicated by the episode review committee will count toward the endpoint.

VT/VF episodes that cannot be adjudicated (due to not saving full episode data or any other reason) will be ignored. Often, these episodes are followed by episodes that can be adjudicated, and since the endpoint is time to first episode, effects on the results from these events will be minimal. In addition, these should be balanced between the comparison groups.

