3.2 Primary Objective: Appropriate Therapy

The primary objective is to demonstrate that appropriate VT/VF therapy rates (shock and ATP) for subjects meeting 1.5 prevention criteria implanted with a Medtronic device (ICD/CRT-D) are equivalent (within 30%) to rates in subjects meeting secondary prevention criteria.

The primary objective will be evaluated by using post-implant time to first appropriate VT/VF therapy (shock and ATP). More specifically, the following hypothesis will be tested:

Hypothesis

H_0 : Hazard ratio of Implanted 1.5 patients to implanted secondary patients ≤ 0.70
 H_a : Hazard ratio of Implanted 1.5 patients to implanted secondary patients > 0.70

Endpoint Definition

The event of interest for this objective is appropriate VT/VF therapy. To qualify as an event, a VT/VF event observed by the ICD/CRT must be adjudicated to be one of the following by the Episode Review Committee:

- Polymorphic VT/VF
- Monomorphic VT
- Non-sustained VT/VF
- Other VT/VF, specify:

Additionally, the episode must have been treated either by ATP, shock, or both by the device.

Performance Requirement

The null hypothesis will be rejected if the one-sided 95% lower confidence bound of the hazard ratio of implanted 1.5 subjects to implanted secondary prevention subjects is greater than 0.70.

Analysis Methods

A Cox proportional hazard model will be used to compare the hazard rates of first appropriate VT/VF therapy between implanted subjects meeting 1.5 prevention criteria and secondary prevention subjects. Because secondary and 1.5 patients are known to be different in many potential covariates, the Cox proportional hazards model will not include any covariates. The one-sided hypothesis test will be performed by computing a 90% two-tailed confidence interval for the hazard ratio between the groups and using the lower limit of this estimated 90% CI as a rejection boundary of the null hypothesis. In particular, if the 90% CI lower limit is greater than 0.7 then the null hypothesis will be rejected.

The analysis will be performed using SAS code similar to:

```
proc phreg data = alldata;
  where group in ('A','C');
  class group (ref = 'A');
  model time2event*eventStatus(0)= group/ rl alpha = 0.1;
  run;
```

Additionally, Kaplan-Meier estimates of the survival curves will be displayed for each prevention criteria group.

Determination of Patients/Data for Analysis

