3.3 Secondary Objective: Mortality

The secondary objective is to compare the mortality rates for patients meeting 1.5 prevention criteria between those implanted with a device (ICD/CRT-D) and those not implanted.

Hypothesis

Although this is an exploratory objective and is not powered, a hypothesis test will be done and compared to an alpha level of 0.05.

H_0 : Hazard ratio of non-implanted to implanted 1.5 patients = 1

H_a : Hazard ratio of non-implanted to implanted 1.5 patients $\neq 1$

Analysis Methods

A Cox proportional hazards model will be used to compare the mortality rates between subjects with device implant and without, in subjects who meet the 1.5 prevention criteria. In addition to the implant/no implant variable, the Cox proportional hazards model will include baseline covariates that are known to be associated with mortality and that might be unbalanced between the groups due to the non-randomized study design. These covariates are:

- age at consent
- sex
- QRS duration
- ischemic cardiomyopathy (yes/no)
- left bundle branch block (LBBB) (yes/no)
- NYHA Classification (treated as an ordinal variable, including 0 for those without HF)
- diabetes (Type 1 or 2 only, gestational not counted) (yes/no)
- LVEF (taken from the 1.5 Visit CRF, if it exists, or from the Baseline CRF)
- syncope qualifying as 1.5 (yes/no)
- NSVT qualifying as 1.5 (yes/no)
- PVCs qualifying as 1.5 (yes/no)

Note that all 3 categorical 1.5 covariates can be found at the end of the 1.5 Criteria CRF. The NSVT and PVC variables on the Baseline CRF do not include the minimum thresholds of 3 consecutive >100 bpm beats for NSVT and 10 or more PVCs per hour.

Country of enrollment was to be included as a covariate according to the CIP, but it will not be included as subjects in the study (who all have medical care) may not have significantly different mortality rates between countries. Also, some countries may have a small number of enrollments. The idea was to have covariates with known mortality risks.

LBBB and diabetes are added covariates from the CIP based on steering committee input. LBBB was added because it is a well-known mortality risk factor. Diabetes was not originally collected in the study, but was added later and is being collected for all subjects, including those enrolled prior to it being added to the Medical History CRF.

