Due to the large sample size, it is likely that some subjects will have covariates missing. To circumvent this problem, multiple imputation methods will be used. More specifically:

- The number of imputed datasets to be created will be 20.
- The imputation of missing values will be done using the fully conditional specification (FCS) method, where the covariates in the imputation model are the same covariates in the Cox proportional model (except the covariate being imputed) plus implant/no implant, the event indicator and the Nelson-Aalen estimator of the cumulative hazard function as suggested by White and Royston (2009).
- The imputation for missing binary variables (e.g., gender) will be done via the FCS logistic regression method, and for missing continuous variables (e.g., QRS) it will be done via the FCS linear regression method.
- Missing NYHA will be imputed via FCS ordinal logistic regression.
- All continuous variables will be standardized before the imputation phase, in order to avoid the FCS linear regression imputing values that are not realistic (e.g., negative LVEF).
- The null hypothesis will be rejected if the pooled p-value for the implant/no-implant covariate is less than 0.05.

The analysis will be performed using SAS code similar to:

```
/*Nelson-Aalen Estimates for Cumulative Hazard Function*/  
  
proc phreg data=alldataneeded1p5 noprint;  
  model SURVTIME*EVENT(0) =;  
  output out=alldataneeded1p5_2 logsurv=logs / method=emp;  
run;  
  
data Alldataneeded1p5_2;  
  set Alldataneeded1p5_2;  
  cumhaz = -logs;  
run;  
  
proc standard data = Alldataneeded1p5_2 mean = 0 std=1 out=  
Alldataneeded1p5_3;  
  var AGE LVEF0 QRS;  
run;  
  
/*Imputation Phase*/  
proc mi data= Alldataneeded1p5_3 n impute = 5 out = mi_alldata_1p5 ;  
class SEXCHAR CMYISCH LBBB NYHA0 DIABETES CRIT15SYNC CRIT15NSVT CRIT15PVC  
GROUP EVENT;  
var AGE SEXCHAR QRS CMYISCH LBBB NYHA0 DIABETES LVEF0 CRIT15SYNC CRIT15NSVT  
CRIT15PVC GROUP CUMHAZ EVENT;  
fcs logistic(SEXCHAR CMYISCH LBBB NYHA0 DIABETES CRIT15SYNC CRIT15NSVT  
CRIT15PVC GROUP EVENT);  
run;  
  
/*Analysis Phase*/  
proc phreg data = mi_alldata_1p5;  
class SEXCHAR CMYISCH LBBB NYHA0 DIABETES CRIT15SYNC CRIT15NSVT CRIT15PVC  
GROUP EVENT;
```

```

model SURVTIME*EVENT(0) = AGE SEXCHAR QRS CMYISCH LBBB NYHA0 DIABETES LVEF0
CRIT15SYNC CRIT15NSVT CRIT15PVC GROUP ;
by _Imputation_;
ods output ParameterEstimates=coxReg_fcs;
ods output Type3=type3table;
run;

/*Pooling Phase*/

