/*      END; */

IF HR_AC>1 THEN OBS_SUCCESS2=1;
ELSE IF FAIL_E12>0 THEN DO;
  IF HR_AC > HR_CE THEN OBS_SUCCESS2=1; ELSE OBS_SUCCESS2=0;
END;
ELSE DO;
  IF HR_AC> 0.9 THEN OBS_SUCCESS2=1; ELSE OBS_SUCCESS2=0;
END;
LABEL OBS_SUCCESS2='SUCESSFUL TRIAL?  SUCCESS BASICALLY DEFINED AS HR OF
C TO A HIGHER THAN E TO C';

*NON-INFERIORITY TEST - MARGINS OF 20, 25, AND 30%;
  IF HRL_AC>0.7 THEN NONINF70=1; ELSE NONINF70=0;
  IF HRL_AC>0.75 THEN NONINF75=1; ELSE NONINF75=0;
  IF HRL_AC>0.8 THEN NONINF80=1; ELSE NONINF80=0;
  IF HRL_AC>0.85 THEN NONINF85=1; ELSE NONINF85=0;
  IF HRL_AC>0.9 THEN NONINF90=1; ELSE NONINF90=0;

*SUPCESS IF 2.0 IS HIGHER THAN 1.0 AND 1.5 IS HIGHER THAN 1.0;
  IF LOGRANKAE<0.05 AND LOGRANKCE<0.05 AND HR_CE<1 THEN SUPSUCCESS=1;
  ELSE IF LOGRANKAE<0.05 AND HR_AE<1 THEN SUPSUCCESS=0.2;
  ELSE IF LOGRANKCE<0.05 AND HR_CE<1 THEN SUPSUCCESS=0.1;
  ELSE SUPSUCCESS=0;

*OPC SUCCESS;
IF FLCL_C12>0.15 THEN OPC15SUCCESS12=1; ELSE OPC15SUCCESS12=0;
IF FLCL_C24>0.15 THEN OPC15SUCCESS24=1; ELSE OPC15SUCCESS24=0;
IF FLCL_C36>0.15 THEN OPC15SUCCESS36=1; ELSE OPC15SUCCESS36=0;
IF FLCL_C12>0.20 THEN OPC20SUCCESS12=1; ELSE OPC20SUCCESS12=0;
IF FLCL_C24>0.20 THEN OPC20SUCCESS24=1; ELSE OPC20SUCCESS24=0;
IF FLCL_C36>0.20 THEN OPC20SUCCESS36=1; ELSE OPC20SUCCESS36=0;
IF FLCL_C12>0.25 THEN OPC25SUCCESS12=1; ELSE OPC25SUCCESS12=0;
IF FLCL_C24>0.25 THEN OPC25SUCCESS24=1; ELSE OPC25SUCCESS24=0;
IF FLCL_C36>0.25 THEN OPC25SUCCESS36=1; ELSE OPC25SUCCESS36=0;

*NARROW CONFIDENCE INTERVAL SUCCESS;
CIWIDTH12=FUCL_C12-FLCL_C12;
CIWIDTH24=FUCL_C24-FLCL_C24;
CIWIDTH36=FUCL_C36-FLCL_C36;
IF CIWIDTH12<0.05 THEN CI05SUCCESS12=1; ELSE CI05SUCCESS12=0;
IF CIWIDTH24<0.05 THEN CI05SUCCESS24=1; ELSE CI05SUCCESS24=0;
IF CIWIDTH36<0.05 THEN CI05SUCCESS36=1; ELSE CI05SUCCESS36=0;
IF CIWIDTH12<0.08 THEN CI08SUCCESS12=1; ELSE CI08SUCCESS12=0;
IF CIWIDTH24<0.08 THEN CI08SUCCESS24=1; ELSE CI08SUCCESS24=0;

```

```

IF CIWIDTH36<0.08 THEN CI08SUCCESS36=1; ELSE CI08SUCCESS36=0;
IF CIWIDTH12<0.10 THEN CI10SUCCESS12=1; ELSE CI10SUCCESS12=0;
IF CIWIDTH24<0.10 THEN CI10SUCCESS24=1; ELSE CI10SUCCESS24=0;
IF CIWIDTH36<0.10 THEN CI10SUCCESS36=1; ELSE CI10SUCCESS36=0;
IF CIWIDTH12<0.12 THEN CI12SUCCESS12=1; ELSE CI12SUCCESS12=0;
IF CIWIDTH24<0.12 THEN CI12SUCCESS24=1; ELSE CI12SUCCESS24=0;
IF CIWIDTH36<0.12 THEN CI12SUCCESS36=1; ELSE CI12SUCCESS36=0;
IF CIWIDTH12<0.15 THEN CI15SUCCESS12=1; ELSE CI15SUCCESS12=0;
IF CIWIDTH24<0.15 THEN CI15SUCCESS24=1; ELSE CI15SUCCESS24=0;

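### The SAP drops the protocol's condition on the mortality test, and also its 400-subject minimum and the word 'spontaneous' for the primary analysis, without saying whether they still apply

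*Protocol*

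**What the plan says.** **Mortality test.** Protocol 12.3.1 compares the test with 0.05 and then adds: "To preserve overall type I error, this test is only valid if the primary endpoint is statistically significant". SAP 3.3 keeps only the first part: "Although this is an exploratory objective and is not powered, a hypothesis test will be done and compared to an alpha level of 0.05". Its decision rule is: "The null hypothesis will be rejected if the pooled p-value for the implant/no-implant covariate is less than 0.05".

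**Minimum for the primary test.** In Protocol 12.2.4, "the hypothesis test will not be performed and a p-value will not be calculated if there are fewer than 400 subjects" in the implanted 1.5 group; event rates and confidence intervals are then reported instead. SAP 3.2 has no minimum: "if the 90% CI lower limit is greater than 0.7 then the null hypothesis will be rejected". SIM.SAS, in the SAP appendix, scores success the same way: "IF HRL_AC>0.7 THEN NONINF70=1; ELSE NONINF70=0". Protocol 12.2.6 states the resulting power: "4800 subjects will have 80% power to reject the null hypothesis". Under Protocol 12.2.7, "the sample size will be re-estimated during the study using the same simulation methods".

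**Endpoint.** Protocol 12.2.4 limits the endpoint to spontaneous episodes that were appropriately treated and adjudicated. SAP 3.2 asks for an adjudicated rhythm category and delivery of ATP or shock, and does not say spontaneous. The SAP's Chagas analysis, which uses the same event, keeps the word.

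**Precedence.** SAP 3.1.3 states an intent that the main publication follow the SAP, and says that the SAP overrides the protocol in some cases, which it does not list. Protocol 12.1 requires an amendment for a change to a principal feature, and a justified account in the study report for any other change.

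**The concern.** A statistician working from SAP 3.3 alone would test mortality at 0.05 whatever the primary result, including when the protocol says the primary test should not be run. That removes the type I error control that the protocol gives as its reason for the condition. Working from SAP 3.2 alone, the same person would run a primary test that the protocol bars in a small 1.5 group, and would find nothing in the endpoint definition to exclude an induced, treated episode.

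The SAP does announce other departures, with reasons: in SAP 3.3 it drops country as a covariate and adds bundle branch block and diabetes. The three rules here get no such statement. The study is not blinded, so these points should be settled before the data are analysed.

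**Working it through.** **1. Reproducing the stated power.** Inputs from Protocol 12.2.6 and SIM.SAS: 4800 enrolled over 2.24 years, 2 years of further follow-up, 60% secondary, half of primary subjects in the 1.5 group, implant rates 57% and 45%, first-year event rate 22.5% then 11.1% a year, attrition 10% a year, hazard ratio 0.91, lower one-sided 95% bound above 0.70. SIM.SAS re-coded in Python and run 20,000 times gives power 80.8% and a mean hazard ratio of 0.904. The SAP appendix gives 80.4% and 0.903. The stated figure reproduces.

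**2. The 400 minimum.**
- Expected implanted 1.5 subjects: 4800 × 0.40 × 0.50 × 0.45 = 432, a margin of 32.
- The count is Binomial(4800, 0.09), since 0.40 × 0.50 × 0.45 = 0.09. P(399 or fewer) = 4.9%.
- In the 20,000 runs: minimum missed 4.8%, performed and successful 77.0%, performed and failed 18.2%. As a check from the SAP's own table, 80.4% × (1 − 0.049) = 76.5%.
- The protocol's condition on mortality is therefore unmet in 4.8% + 18.2% = 23.0% of trials. In those trials the SAP as written still permits a mortality claim.
- In a separate 10,000-run simulation, 3.9% of trials met the SAP's success rule although the protocol barred the test.
- At the same 9% share, P(fewer than 400) would be 11.5% at 4700 enrolled and 57.6% at 4400. The sponsor may lower the sample size at re-estimation, and SIM.SAS would not register the minimum.

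**3. The mortality condition.** The primary test has one-sided alpha 0.05; the mortality test has two-sided alpha 0.05.

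| Situation (tests independent) | Without the condition | With it |
|---|---|---|
| Both nulls true, primary HR exactly 0.70: any false claim | 1 − 0.95² = 9.75% | 5% |
| Same: false mortality claim | 5% | 0.05 × 0.05 = 0.25% |
| Primary HR 0.91, mortality null true: false mortality claim | 5% | 0.05 × 0.770 ≈ 3.9% |

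Under any dependence the first entry cannot exceed 0.05 + 0.05 = 10%. Independence is a fair approximation although implanted 1.5 subjects enter both tests. A joint simulation of 20,000 runs (HR 0.70, equal mortality of 25.7% at 3 years in both 1.5 groups, unadjusted Cox models) gave 5.1% for the primary, 5.0% for mortality and 9.8% for either, with correlation 0.00 between the test statistics. If the true primary hazard ratio is further below 0.70, the 9.75% falls toward 5%.

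**4. 'Spontaneous'.** SAP 3.2 carries over the sentences that flank this rule in Protocol 12.2.4 (censoring at the last interrogation; unadjudicated episodes ignored) but not the rule itself. The documents give no rate of induced, treated episodes, so neither size nor direction can be computed.

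**The case against.** **Silence is not repeal.** The SAP was developed from version 1.0 of the protocol, Protocol 12.1 sets a route for changes, and what SAP 3.1.3 lets override the protocol is the methods that the SAP details. It details no alternative multiplicity rule, minimum count or treatment of induced episodes. A reader might infer that the sponsor withdrew the three rules; the documents do not support that. The protocol rules may well remain in force. What stands is that SAP 3.3 and SAP 3.2 give unconditional rejection rules that contradict the first two, and nothing says which governs.

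**Mortality is exploratory.** Both documents call it exploratory and unpowered, and the 5% is two-sided, so a false claim of benefit has a 2.5% chance. That limits the harm. But the protocol uses the same word and still imposes the condition, expressly to protect type I error.

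**9.75% is a worst case.** Correct: it needs a true hazard ratio of exactly 0.70. At 0.91 the difference is 5% against about 3.9%.

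**Later implants help.** Subjects who first refuse and are implanted later enter the primary analysis if they are 1.5 at implant (Protocol 6.10.1 and 12.2.5), and SIM.SAS does not model them. Their rate is not given. If 1%, 2% or 5% of the roughly 528 initial 1.5 refusers (4800 × 0.20 × 0.55) were implanted later, P(fewer than 400) would fall to 2.8%, 1.5% or 0.2%. So 77% holds under the SIM.SAS assumptions, not as a forecast.

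**Missing interrogations.** A reader might infer that SAP 3.2's one-interrogation requirement erodes the 400 count further. The documents do not support this: the protocol counts the implanted 1.5 group, and Protocol 6.9.2 requires an interrogation at implant.

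**The episode committee may exclude induced episodes anyway.** Possibly; its charter is not in the documents. The word's survival in the Chagas analysis suggests a drafting slip.

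**Conclusion.** The three omissions are real and should be repaired before analysis. The mortality condition matters most, because the SAP's rule, followed as written, breaks an error control that the protocol states. For these two tests the cost is at most 9.75% against 5% (both nulls true, primary hazard ratio exactly 0.70, independence; never above 10%). At the planning hazard ratio, a false mortality claim has a 5% chance against about 3.9%.

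The stated 80% power is computed correctly but takes no account of the protocol's own 400 minimum; with it, the figure is about 77% under the SIM.SAS assumptions, before any later implants. A reader might conclude that the sample size is wrong or that more subjects must be enrolled. That does not follow: the shortfall is about 3 points, later implants would reduce it, and the enrollment and implant shares are to be replaced with study data at re-estimation.

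The omission of 'spontaneous' is an inconsistency of unknown effect.

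**What to change.** 1. **SAP 3.3**, add: *The mortality test is interpreted at 0.05 only if the primary null hypothesis is rejected; otherwise, including when the primary test is not performed, its p-value is nominal.* Label the added 1.0 mortality comparison and the three Chagas tests (1.0, 1.5 and secondary) as nominal, since the 5% above covers only the primary and 1.5 mortality tests.
2. **SAP 3.2**, carry over the 400-subject rule as the protocol words it, counting subjects in the implanted 1.5 group. Do not add the one-interrogation requirement to that count, which would make a stricter rule than the protocol's.
3. **SAP 3.2 endpoint definition**, specify a spontaneous VT/VF event, to match Protocol 12.2.4 and the Chagas analysis.
4. **Power**, state that the 80% at 4800 does not allow for the 400 minimum and is about 77% with it under the SIM.SAS assumptions. Add GROUPC_SS>=400 to the success condition used at re-estimation.

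If the sponsor does mean to override any of these rules, SAP 3.1.3 should list it with a reason, and Protocol 12.1 then decides whether an amendment is needed. Keeping the rules costs a few sentences in the SAP and one condition in the program: no new data, no protocol amendment and no extra subjects.
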